2.4 Imputation of Incomplete Dates

Incomplete or partial dates will be imputed (where appropriate, and will follow Virtual Data Warehouse (VDW) imputation rules – refer to VDW MAP M8) to decide on the inclusion or exclusion of related events in the summary tables. Each incomplete date will be split into its day, month, and year components, and an imputation rule will be applied. However in data listings, the dates as available in the database should be listed (without imputation).

General imputation rules from the VDW MAP M3, draft version 3.0 are given below.

Specific imputation rules may apply to certain panels (e.g. concomitant medications) and are described in the relevant sections. If no imputation rules are described then the general imputation rules apply to partially missing or impossible dates:

- If the year is missing or impossible (e.g. 12-Jan-1911), then the date will be imputed as missing.
- If the year is not missing and possible, but the month is impossible or missing (e.g. 17-XXX-2010), then the year will be kept and July 1st will be imputed (1-July-2010).
- If the year and the month are not missing and possible, but the Day is impossible or missing (e.g. 31-FEB-2009), then the year and month will be kept, the 15th will be imputed (15-FEB-2009).

2.5 Analysis sets

The following analysis sets will be defined.

- **Enrolled set:** The enrolled set will include all patients who entered the long-term follow-up study part I (excludes long-term follow-up study screen failures), but will exclude patients with protocol deviation severity code of 8 (8=exclude from all analyses) in the long-term follow-up study part I.
- **Safety set:** The safety set will include all patients who entered the long-term follow-up study part I and received at least one dose of fingolimod in any study, but will exclude patients with protocol deviation severity codes of 5 (5=exclude from all safety analyses) and 8 (8=exclude from all analyses) in the long-term follow-up study part I. Note that all data reported in the long-term follow-up study part I will be analyzed, including assessments or events which started before the long-term follow-up study part I.
- **Fingolimod safety set:** The fingolimod safety set will include all patients who entered the long-term follow-up study part I and received at least one dose of fingolimod in any study, but will exclude patients with protocol deviation severity codes of 5 (5=exclude from all safety analyses) and 8 (8=exclude from all analyses) during the core study prior to entry to the long-term follow-up study part I. For patients with such protocol deviations after the core study, record level data associated with the protocol deviations will be excluded from the analysis.

- **Fingolimod full analysis set:** The fingolimod full analysis set will include all patients who entered the long-term follow-up study part I and received at least one dose of fingolimod in any study but will exclude patients with protocol deviation severity codes of 0 (0=exclude from all efficacy analyses) and 8 (8=exclude from all analyses) during the core study prior to entry to the long-term follow-up study part I. For patients with such protocol deviations after the core study, record level data associated with the protocol deviations will be excluded from the analysis.
- **Follow-up set:** The follow-up set will consist of all patients in the safety set who have any follow-up visit data or at least one safety record after the study drug discontinuation. It will be used for summary of adverse events and concomitant medications with occurrences after last dose of fingolimod only.

Patient disposition, core study, protocol deviations, analysis sets, demographics, and baseline and history information will be summarized based on the enrolled set. Efficacy analyses will be summarized based on the fingolimod full analysis set. Safety summaries that include only long-term follow-up study part I data will be based on safety set, while other safety assessments that include data from the first dose of fingolimod among all studies, will be summarized based on fingolimod safety set.

A summary of the number and percentage of patients in each analysis set (enrolled set, safety set, fingolimod safety set, fingolimod full analysis set, and follow-up set) will be summarized. Percentages will be based on the enrolled set. A listing of patient assignment into each analysis set will also be displayed.

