### **Safety set**

The Safety set will consist of all patients that received at least one dose of study drug in this long-term follow-up study.

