### **Fingolimod safety set**

The fingolimod safety set will include all patients who entered the long-term follow up study and received at least one dose of fingolimod in any study, i.e., in the original core/extension MS studies or this long-term follow up study.

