2.5 Analysis sets

The following analysis sets will be defined. Analyses done on the fingolimod safety set and fingolimod full analysis set summarize all data starting from first dose of fingolimod among all studies, while other analysis sets generally summarize all data from the study part 2 only.

- **Enrolled set:** The enrolled set will include all patients who entered the study part 2 (excludes long-term extension study screen failures), but will exclude patients with protocol deviation severity code of 8 (8=exclude from all analyses) in the study part 2.
- **Safety set:** The safety set is a subset of the fingolimod safety set and will include all patients who entered the study part 2 and received at least one dose of fingolimod in any study, but will exclude patients with protocol deviation severity codes of 5 (5=exclude from all safety analyses) and 8 (8=exclude from all analyses) in the study part 2. Note that all data reported in the study part 2 will be analyzed, including assessments or events which started before the study part 2, unless otherwise specified. For example, adverse events which may have been continuing at the end of the long-term follow-up

study part 1 may be recorded in the study part 2 database with updated end date. These adverse events will be reported in listings and summarized if event occurs after first dose of fingolimod among all studies.

- **Fingolimod safety set:** The fingolimod safety set will include all patients who entered the study part 2 and received at least one dose of fingolimod in any study, but will exclude patients with protocol deviation severity codes of 5 (5=exclude from all safety analyses) and 8 (8=exclude from all analyses) during the core study prior to entry to the long-term follow-up study part 1. For patients with such protocol deviations after the core study, record level data associated with the protocol deviations will be excluded from the analysis.

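### Both SAPs drop treated patients and single records from the safety sets because of protocol deviations, although the protocol defines these sets by dosing alone; the documents do not allow the effect to be sized

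*SAP*

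**What the plan says.** **Protocol, section 9.1.** For the Safety set: "The Safety set will consist of all patients that received at least one dose of study drug in this long-term follow-up study". The fingolimod safety set, by contrast, "will include all patients who entered the long-term follow up study and received at least one dose of fingolimod in any study". Neither definition mentions deviations. Section 9.4.1 uses the Safety set for data from this study only, and the fingolimod safety set for data from the first fingolimod dose onward. Section 9.4.1.1 bases the adverse event rates per 100 patient-years on the fingolimod safety set and the percentage tables on the Safety set. It also provides for a listing of every SAE and death noted in the study.

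**SAP Part I, section 2.5.** The Safety set needs a fingolimod dose in any study, and it "will exclude patients with protocol deviation severity codes of 5 (5=exclude from all safety analyses) and 8 (8=exclude from all analyses) in the long-term" (the sentence goes on to name Part I). The fingolimod safety set removes patients with code 5 "and 8 (8=exclude from all analyses) during the core study prior to entry to the long-term follow-up study part I". Where a deviation of this kind arises later, "record level data associated with the protocol deviations will be excluded from the analysis".

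**SAP Part 2, section 2.5.** The same rules return. The Safety set "will exclude patients with protocol deviation severity codes of 5 (5=exclude from all safety analyses") or code 8 in Part 2, and it is stated to be a subset of the fingolimod safety set.

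**Listings.** SAP Part I section 9.1.2.1 and SAP Part 2 section 9.1.2.1.1 give the listings of SAEs, deaths and neoplasms for the Safety set.

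**The concern.** Safety is the primary objective (Protocol section 2.1) and no inferential analysis is planned (section 9.4.1). The descriptive rates and listings are therefore the main result. The protocol's background section says that further long-term data are needed on rare or time-dependent events, and there a few lost cases matter most.

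The SAPs narrow the population on which the primary objective rests. They do not say which deviations receive code 5 or 8, what makes a record associated with a deviation, or why the protocol's definitions were changed. No analysis of all dosed patients with all their records is planned alongside. Set membership is fixed before database lock (Protocol section 9.1), but treatment is open-label, and the documents do not say that codes are assigned without sight of the adverse events.

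**Working it through.** The plan states no figure to reproduce: there is no sample size formula, alpha or power. The check is a comparison of rules, then an illustration of scale.

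**1. Which rule reaches which output**

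| Output | Set | Removed |
|---|---|---|
| Part I event percentages; SAE, death and neoplasm listings (SAP Part I 9.1.2.1) | Safety set | whole patients with code 5/8 in Part I; no record deletion |
| Part I incidence rates from first fingolimod dose (9.1.2.2) | Fingolimod safety set | whole patients with code 5/8 in the core study; associated records for later deviations |
| Part 2 percentages, listings and incidence rates (SAP Part 2 9.1.2.1.1, 9.1.2.1.2) | Part 2 Safety set | whole patients with code 5/8 in Part 2 or, through the subset rule, in the core study |
| Part 2 yearly-interval tables (9.1.2.2; set by the general rule in 2.5) | Fingolimod safety set | as for Part I incidence rates |

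Under the protocol, the last column would be empty in every row.

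**2. Direction when a record is dropped.** SAP Part I section 9.1.2.2 defines the rate as patients with at least one event, divided by patient-years at risk, times 100. A patient with the event contributes time to its first occurrence. A patient without it contributes time to last dose + 45 days. If the event record goes and the dosing dates stay, the numerator falls by one and the denominator grows. If a later event of the same kind remains, the patient is still a case but contributes more time. Either way the rate can only fall.

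**3. Illustration of size.** Inputs from the documents: 4,150 enrolled (Amendment 11) and 0.4% with macular edema (Protocol Appendix 7), so 0.004 × 4,150 = 16.6, taken as 17 cases. Assumed: mean follow-up 5 years and event at 0.3 years. Time at risk without the event is 5 + 45/365.25 = 5.123 years.

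- All records kept: 17 / (4,133 × 5.123 + 17 × 0.3) × 100 = 0.0803 per 100 patient-years.
- One record dropped: 16 / (4,134 × 5.123 + 16 × 0.3) × 100 = 0.0755, a fall of 5.9%.
- Two dropped: 0.0708, a fall of 11.8%.
- Four dropped: 0.0613, a fall of 23.6%.

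With mean follow-up of 3 or 7 years, or the event at mid-follow-up, the relative falls are the same to within 0.1 percentage point.

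**4. Direction when a whole patient is removed.** Numerator and time both go. If the removed patients are all cases, the falls are almost the same: 5.9%, 11.8% and 23.5% for 1, 2 and 4. If they include no case, the rate rises. Removing 83 event-free patients (an assumed 2% of 4,150) gives 17 / (4,050 × 5.123 + 17 × 0.3) × 100 = 0.0819, up 2.0%. The direction depends on who is removed.

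**5. How many patients.** This is not given. If 0.1% to 5% of 4,150 carried a code, 4 to 208 treated patients would be affected. The 4,150 is enrolment, not a safety-set count.

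**6. Minor point.** The SAP Safety sets accept a dose in any study. The protocol requires one in D2399 (section 9.1) or, for the Part Two subgroup, one after completing Part One (section 9.1.1). Patients never dosed in the relevant part can therefore enter the denominator.

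**The case against.** **The codes may be harmless.** They might cover only cases such as missing consent, which any plan would exclude. The documents neither say so nor rule it out. A reader might infer that the exclusions hide safety-related deviations, such as use of prohibited immunosuppressants or dosing despite an exclusion criterion. Nothing in the documents links those to code 5 or 8, and eligibility or consent deviations arise at or before entry rather than after dosing. The supported criticism is that the exclusions are undefined, unjustified and contrary to the protocol.

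**The rates may not be biased downward.** For whole-patient removal this objection stands (step 4). For dropped event records it stands only if the deleted records also include the dosing dates that set time at risk, and the SAP does not define what is deleted.

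**Part I incidence rates keep D2399 deviators.** This is correct. A deviation in D2399 costs the fingolimod safety set the associated records, not the patient. The Part I Safety set works the other way: it loses the patient, but otherwise analyzes all data reported in Part I.

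**Exclusions are reported.** Set membership is listed, and exclusion-causing deviations are summarized (SAP Part I sections 2.5 and 4). That shows some of the loss but restores no event. The summaries use the enrolled set, which itself drops patients with code 8 in Part I.

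**Deaths are covered elsewhere.** The cause-of-death summary speaks of all deaths recorded in the D2399 database. That sentence sets the onset window; section 2.5 still bases such summaries on the Safety set. The separate listings for patients from D2312 and D2402 use the enrolled set, so there only code 8 removes a patient.

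**Never-dosed patients dilute the percentages.** A reader might make much of this. It is minor: the percentage tables also count events with onset from the first fingolimod dose in any study, so such patients can add to the numerator too, and their number is not given.

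**Conclusion.** The contradiction is established from the texts. The protocol's safety sets are all dosed patients, while both SAPs remove patients and records for deviations, in the sets that carry the primary safety results and the SAE and death listings. Through the subset rule, a deviation in a core study years earlier can remove a treated patient from every Part 2 Safety-set summary.

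The size of the effect is unknown. The falls of about 6%, 12% and 24% show what losing 1, 2 or 4 of 17 cases would do; they do not predict that any will be lost. They rest on the assumed follow-up and event times and on the 0.4% taken from macular edema. A downward effect is certain only for dropped event records with time at risk kept. A reader might conclude that the plan makes the safety profile look better; for whole-patient removal the documents do not support that, because nothing is known about the excluded patients' event rates.

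**What to change.** - Define each Safety set as all patients with at least one dose in the relevant part of D2399.
- Define the fingolimod safety set as all entrants with at least one fingolimod dose in any study.
- Make no exclusion of patients or records for deviations, except where the data may not legally be used (for example, no valid consent), and state that exception in the SAP.
- Remove the rule that makes a core-study deviation disqualify a patient from the Part 2 Safety set.
- List all SAEs and deaths regardless of set membership.
- Report deviations descriptively, including those of any patient left out of the enrolled set.

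The cost is a change of SAP wording and the removal of a filter; no new data are needed. Rates may become slightly less favourable.

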## Glossary of terms

Assessment	A procedure used to generate data required by the study
Enrollment	Point/time of patient entry into the study; the point at which informed consent must be obtained (i.e. prior to starting any of the procedures described in the protocol)
Investigational drug	The study drug whose properties are being tested in the study; this definition is consistent with US CFR 21 Section 312.3 and is synonymous with “investigational new drug.”
Medication number	A unique identifier on the label of each study drug package in studies that dispense study drug using an IVR system
Patient number	A number assigned to each patient who enrolls in the study. When combined with the center number, a unique identifier is created for each patient in the study.
Period	A minor subdivision of the study timeline; divides phases into smaller functional segments such as screening, baseline, titration, washout, etc.
Premature patient withdrawal	Point/time when the patient exits from the study prior to the planned completion of all study drug administration and assessments; at this time all study drug administration is discontinued and no further assessments are planned
Stage	A major subdivision of the study timeline; begins and ends with major study milestones such as enrollment, randomization, completion of treatment, etc.
Stop study participation	Point/time at which the patient came in for a final evaluation visit or when study drug was discontinued whichever is later
Study drug	Any drug administered to the patient as part of the required study procedures; includes investigational drug and any control drugs
Study drug discontinuation	Point/time when patient permanently stops taking study drug for any reason; may or may not also be the point/time of premature patient withdrawal
Variable	Information used in the data analysis; derived directly or indirectly from data collected using specified assessments at specified timepoints

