By June 2016, investigators must determine commercial Gilenya eligibility for all active study patients (i.e., reimbursed for commercial Gilenya). Patients able to obtain commercial Gilenya will then have their End of Study (Part One) visit and exit the study, regardless of their post-study treatment decision (i.e., continuing on Gilenya commercially or transitioning to another treatment option). Patients discontinuing or completing the study at Part One who do not continue on commercial Gilenya must return for two follow-up study visits, 3-months and 6-months post-last dose of fingolimod. Patients who choose to continue on commercial Gilenya outside the study are exempted from the follow-up visits. Patients not eligible for reimbursed, commercial Gilenya will be offered continued study participation in Part Two until their scheduled study visit closest to 30-Jun-2018 (+/- 30 day visit window), with a reduced assessment schedule (see protocol Table 6-2), for the purpose of collecting additional long-term safety and tolerability data in support of the primary study objective. Patients discontinuing or completing the study after entering Part Two who do not continue on commercial Gilenya must return for one follow-up study visit, 3-months post-last dose of fingolimod. Patients who choose to continue on commercial Gilenya outside the study are exempted from the follow-up visit.

The duration of treatment of a patient in this trial is dependent on which study the patient participated in previously as well as the availability of reimbursement for commercially available fingolimod in the respective country. The study part I is planned to end by 30-Jun-2016 in order to collect 6 months or more of long-term safety data for the majority of Phase II/III patients. Guidance regarding scheduling of the Study Completion visit is provided in order to streamline the study closure processes, specifically designating the Study Completion visit to occur at or shortly after sixty months of study participation for those patients who would reach 60 months by 30-Jun-2016. Patients not reaching 60 months by 30-Jun-2016 will have their study completion on or around 30-Jun-2016 (+/- 30 day visit window), and patient who have already reached 60 months should have their Study Completion visit at their next six monthly visit, or 30-Jun-2016, whichever comes first.

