2.3.2 Study day

The day of first administration of fingolimod study drug is defined as *Day 1*. Day 1 does not need to occur in the long-term follow-up study.

All other study days will be labeled relative to Day 1. Thus, study day for a particular event date on or after Day 1 is calculated as: (*Date of event – Date of first dose of fingolimod study drug + 1*). An event that occurs prior to Day 1 is calculated as: (*Date of event – Date of first dose of fingolimod study drug*).

In addition to calculating study day with respect to the first dose date of fingolimod drug across all studies, study day will also be calculated relative to the first dose date of fingolimod during the long-term follow-up study.

The number of days after permanent study drug discontinuation will be calculated as (*Date of event – Date of last dose of fingolimod study drug*).

The duration of an event will be calculated as (*Event end date – Event start date + 1*). Day 0 will not be used.

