9.1.2.1 Adverse events during long-term follow-up study part I

Adverse events reported during the long-term follow-up study part I will be summarized for the safety set. Unless otherwise specified, all non-serious adverse events recorded in the CFTY720D2399 database with onset on or after first dose date of fingolimod among all studies to last dose date of fingolimod + 45 days are included. All serious adverse events

(SAEs) recorded in the CFTY720D2399 database with onset on or after the first dose date of fingolimod among all studies are also included in the summaries.

Adverse events reported during the long-term follow-up study part I will be summarized by primary system organ class (SOC) and preferred term (PT), and will show the number and percentage of patients with at least one adverse event in each SOC or PT category. Similarly, adverse events by study drug relationship (AEs suspected to be study drug related, AEs not suspected to be study drug related, and AEs regardless of study drug relationship), SAEs, SAEs by study drug relationship, suspected study drug related AEs, and AEs leading to study drug discontinuation will also be summarized by SOC and PT.

AEs and SAEs which are not considered to be known effects of fingolimod treatment (i.e., excluding those listed in the most recent version of Core Data Sheet), will be summarized by PT only.

To determine which AEs occur after discontinuation of fingolimod treatment, all AEs reported with onset date after the last dose of fingolimod until the end of the long-term follow-up study part I will be summarized by SOC and PT for the follow-up set.

Principal cause of death during the long-term follow-up study part I will be summarized by SOC and PT. All deaths recorded in the CFTY720D2399 database with onset on or after the first dose date of fingolimod (among all studies) will be included in the summary.

All information pertaining to any AE with severity information, SAEs, AEs leading to study drug discontinuation, deaths and neoplasms system organ class events that reported during the long-term follow-up study part I will be listed for the safety set. Additionally, adverse events, SAEs and all deaths recorded during the long-term follow-up study part I will be listed for the subgroup of patients from studies D2312 and D2402 in the enrolled set.

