2.5.1 Subgroups

The following subgroups are defined for subject disposition and AE analysis during fingolimod treatment period:

1. Duration of fingolimod treatment up to the end of the study part 2 (yearly interval):
 - Year 1 subgroup: patients on fingolimod treatment > 0 year (≥ 1 day)
 - Year 2 subgroup: patients on fingolimod treatment > 1 year (≥ 361 days)
 - Year 3 subgroup: patients on fingolimod treatment > 2 year (≥ 721 days)
 - Year 4 subgroup: patients on fingolimod treatment > 3 year (≥ 1081 days)
 - Year 5 subgroup: patients on fingolimod treatment > 4 year (≥ 1441 days)

- Year N subgroup: patients on fingolimod treatment > N -1 year ($\geq (N - 1) \times 360 + 1$ days)

3 Protocol Deviations

The number and percentage of patients in the enrolled set with each protocol deviation in the study part 2 will be displayed by protocol deviation category. Additionally, patients with at least one protocol deviation during the study part 2 and patients with at least one protocol deviation causing exclusion from any analysis set (deviation severity codes 0, 5, or 8) will be summarized.

The protocol deviation data will be listed as well.

Additionally, the investigator comments during the study part 2 will be listed.

4 Patient Disposition

All screen failures in the study part 2 will be listed along with their primary reason for failing screening.

The number and percentage of patients who completed the study part 2, and who discontinued the study part 2, along with the primary reason for discontinuation, will be summarized for the enrolled set. The number and percentage of patients who are expected to have month 3 follow-up visit and who returned will also be summarized. The number and percentage of patients who move to commercial fingolimod after study completion will also be included.

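### The follow-up set does not exclude patients who continue fingolimod commercially, so the tables of events after stopping fingolimod can include on-drug patients, selected partly by having had an event

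*SAP*

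**What the plan says.** Section 2.5 of the Part I SAP and section 2.5 of the Part 2 SAP both define the follow-up set as "all patients in the safety set who have any follow-up visit data or at least one safety record after the study drug discontinuation". On its use they say: "It will be used for summary of adverse events and concomitant medications with occurrences after last dose of fingolimod only". Neither defines a safety record or sets a condition on fingolimod use after the last study dose.

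The Part I SAP, section 9.1.2.1, gives the purpose of the AE table: "To determine which AEs occur after discontinuation of fingolimod treatment, all AEs reported with onset date after the last dose of fingolimod", up to the end of Part I, are tabulated for this set. Section 9.1.2.1.1 of the Part 2 SAP does the same for Part 2. Section 7.3 of each SAP uses the set to see whether particular treatments are needed once fingolimod is stopped. The AE tables of Part I section 9.1.2.1 "will show the number and percentage of patients with at least one adverse event in each SOC or PT category".

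On follow-up visits, the Part I SAP Overview says: "Patients who choose to continue on commercial Gilenya outside the study are exempted from the follow-up visits". Footnote 14 of Protocol Table 6-1 and footnote 10 of Table 6-2 likewise reserve these visits for patients who do not go on with fingolimod in any setting.

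Both SAPs count, under Patient Disposition, the patients expected to have follow-up visits and those who returned. The Part 2 SAP, section 4, adds: "The number and percentage of patients who move to commercial fingolimod after study completion will also be included".

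**The concern.** The tables are about stopping fingolimod, but the set is built on stopping study drug. For a patient who moves to commercial supply these differ: study drug ends and exposure to fingolimod does not.

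Such a patient has no follow-up visits and enters the set only if some safety record falls after the last study dose. If that record is an event, the patient joins numerator and denominator together, while an otherwise identical patient without an event may stay out. If the record is a routine measurement, the patient joins the denominator with almost no follow-up time. Either way, a percentage meant to describe patients off the drug is computed partly on patients still taking it, and events on drug may be read as events after withdrawal. The medication table shares the problem.

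**Working it through.** The documents state no figure for this set, so there is none to reproduce. The first two steps compare the rules. The last two are illustrations on assumed counts.

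**1. Does a switcher count as discontinued?** Yes. The Protocol glossary defines study drug discontinuation as "Point/time when patient permanently stops taking study drug for any reason", and section 2.3.2 of both SAPs counts days after discontinuation from "Date of last dose of fingolimod study drug". Continued commercial use does not alter either.

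**2. What record can a switcher have after that date?**
- Follow-up visit data: none by design.
- SAEs: Protocol section 7.2 requires every SAE to be reported until six weeks after participation stops, and later ones if a causal link to study drug is suspected.
- Non-serious AEs: these are sought at visits (Protocol section 7.1), so for a switcher mainly between the last capsule and the completion visit.
- Vital signs or laboratory values at the completion visit, if dated after the last capsule and if they count as safety records. The SAPs do not say.

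**3. Direction.** Let N be the patients who truly stop and have data, p their AE proportion, C the switchers, r the share of switchers who enter the set, and a the share of those entrants with an AE after the last dose. Then

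shown percentage = (N·p + C·r·a) / (N + C·r), and shown − p = C·r·(a − p) / (N + C·r).

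Entry through an event has a = 1, so the table reads too high. Entry through routine measurements has a small; when a is below p, the table reads too low.

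**4. Size.** For entry through SAEs alone, the nearest documented figure is the 10.5% SAE incidence on 0.5 mg/day in Protocol section 1.1. The period it covers is not given there; I assume one to two years. Six weeks is 42 days:
- one year: 10.5% × 42/365.25 = 1.2%
- two years: half of that, 0.6%

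For entry through completion-visit records I assume r = 50% and a = 2%. N, p and C are assumptions throughout.

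| N, p, C | SAE entry, r = 0.6% | SAE entry, r = 1.2% | Completion-visit entry |
|---|---|---|---|
| 500, 30%, 2,000 | (150+12)/(500+12) = 31.6% | (150+24)/(500+24) = 33.2% | (150+20)/(500+1,000) = 11.3% |
| 600, 20%, 3,000 | (120+18)/(600+18) = 22.3% | (120+36)/(600+36) = 24.5% | (120+30)/(600+1,500) = 7.1% |
| 300, 10%, 3,000 | (30+18)/(300+18) = 15.1% | (30+36)/(300+36) = 19.6% | (30+30)/(300+1,500) = 3.3% |

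With four or five switchers per patient who stops (first two rows), SAE entry adds 1.6 to 4.5 points. With ten (third row) it adds 5.1 to 9.6. The two routes can also offset each other.

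**The case against.** The case for leaving the definition alone has five parts.

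- **Little is collected after exit.** Switchers leave the study, and only SAEs must then be reported, for six weeks. This stands. A reader might assume that 5% or 10% of switchers enter with an event; with 500, 30% and 2,000 that gives (150+100)/600 = 41.7% or (150+200)/700 = 50.0%. The collection rules do not support entry rates that high.
- **The end-point is unclear.** The Part I table runs to the end of Part I. If that means each patient's own exit visit, post-exit SAEs mostly drop out of the numerator. This also stands as an uncertainty, though the SAP does not settle it, and a patient with such an SAE could still be in the denominator.
- **The protocol promise is met.** Protocol section 9.4.3 promises follow-up safety data after study drug discontinuation, which this set provides. That is right, so a reader should not infer a breach of the protocol. The mismatch is with the SAPs' own stated purpose.
- **A set limited to patients with data is sensible.** This stands too. A reader might infer that everyone who stopped should be included whether or not seen again. Patients who never return would then count as AE-free: if 20% do not return (an assumption), a true 30% would show as 0.80 × 30% = 24%.
- **Listings help.** Set membership and AEs are listed, and Part 2 tabulates moves to commercial drug. This allows reconstruction by hand but does not correct the tables.

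**Conclusion.** The point holds as a mismatch between a written rule and its stated purpose, in both SAPs. Nothing in the definition keeps out patients who continue fingolimod commercially, and their way in depends partly on having an event.

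The documents do not establish size or direction, because they give neither the number of switchers nor a definition of a safety record. If only SAEs in the six-week window bring switchers in, the inflation is probably a few points. That rests on the assumed one-to-two-year base for the 10.5% figure and on about four or five switchers per patient who stops; it would be larger if few patients stop. If completion-visit records qualify, the percentage falls instead.

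A reader might infer that the study's main safety results are compromised. They are not affected by this definition: the AE incidence rates and yearly-interval tables do not use the follow-up set, and no test or sample size depends on it. Only the descriptive AE and medication tables for the period after the last dose are touched.

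**What to change.** In section 2.5 of both SAPs:

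1. Restrict the follow-up set to safety-set patients who do not continue fingolimod after the last study dose (commercially, in another study or, for the Part I analysis, in Part Two) and who have follow-up visit data or at least one safety record after that dose.
2. State that a record from the study completion or premature discontinuation visit does not by itself qualify.
3. Beside the tables, show the number expected to have follow-up and the number with data, so that non-returners are visible and are not counted as AE-free.
4. List AEs after the last study dose separately for patients who continue fingolimod.

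The cost is one definition in each SAP, a line of counts and a split listing. Both disposition sections already need the count of patients expected to have follow-up visits, which depends on whether fingolimod is continued. Part 2 also already tabulates moves to commercial drug; Part I does not, so there the expected-follow-up status has to serve. No new data collection appears necessary.
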